## **C.15. Methodological challenges.** We have considered the following methodological challenges:

- 1. There is the possibility of differential compliance with the protocol for instance, if the HF patient has an exacerbation that distracts the caregiver and interferes with the intervention or assessments. We will allow some flexibility in the timing of ViCCY sessions to accommodate such events and increase the generalizability of study results. Caregivers in the ViCCY arm will be able to schedule calls with the RN coach during day, evening, and weekend hours to limit stress from study participation. For both arms, we will allow data collection calls to be completed up to two weeks before or after the planned contact date to accommodate schedules. We will collect data on cancelled and delayed events for later analysis and adjust for delays and the dose of intervention received in analyses.
- 2. A threat to validity includes the potential for the control group to receive a level of natural support sufficient to interfere with our ability to detect treatment effects from ViCCY. We will interview participants about naturally occurring support so that we can adjust for this in the analysis if needed.
- 3. We may have difficulty enrolling the most stressed and burdened caregivers who may see the trial as one more demand; however, in pilot testing we found that caregivers were grateful for the support.
- 4. It is possible that the patient could die during the year in the study; half of all HF patients die within 5 years. 11 Should this occur, the caregiver will be dropped from the study.

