Using a randomized controlled trial (RCT) design, we will enroll informal HF caregivers with poor self-care (Health Self-Care Neglect scale score ≥2), randomizing them 1:1 to an intervention or control group. Both groups will receive standard care augmented with Health Information (HI) delivered through the Internet, but the ViCCY caregiver group will also receive 10 front-loaded coaching support sessions tailored to individual issues. The control group will have access to the same HI resources over the same interval, using the same Internet program, but without coaching support. At baseline and 3, 6, 9, and 12 months, we will collect self-reported data on self-care, stress, coping, and health status. At 6 months, we will compare the efficacy of ViCCY (HI plus coaching) to HI alone to assess intervention efficacy using intent-to-treat analysis. Our pilot data suggest that addition of support provided by the health coach will make ViCCY more efficacious than HI alone. A sample of 250 caregivers (125/arm) will provide >90% power to detect significant differences between the groups on the primary outcome of self-care (Aim 1). We will collect quality adjusted life years (QALYs) and health care resource use in caregivers over 12 months to assess cost-effectiveness of ViCCY (Aim 2). To explore the effect of caregiver outcomes on HF patients' outcomes over a 12-month period (Aim 3) and knowing that not all HF patients will participate, we will consent a subgroup of the HF patients cared for by these caregivers (at least 40 dyads). We have the following Specific Aims:

- Aim 1: To compare the efficacy of ViCCY vs. HI alone in improving self-care. We hypothesize that, at 6 months after enrollment, caregivers randomized to ViCCY vs. HI alone will have **H1a**: Improved self-care measured with the Health Self-Care Neglect scale (*primary outcome*); **H1b**: Less self-reported stress measured with the Perceived Stress Scale (*secondary outcome*); **H1c**: Better coping measured with the Ways of Coping Questionnaire, short form(*secondary outcome*); and **H1d**: Better perceived mental and physical health status measured with the SF-36(*secondary outcome*).

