ViCCY over 6 months. Assessments of self-care, perceived stress, coping, and health status will be conducted at baseline (after enrollment but prior to randomization) and by phone at 3, 6, 9 and 12 months. Using contrasts within a mixed-effect modeling framework, we will assess intervention efficacy at 6 months using intention-to-treat analysis. We chose to provide 10 health coaching sessions based on our pilot data and literature demonstrating that a shorter duration of health coaching is not routinely effective. Ye chose to assess the primary aim at 6 months based on prior psychosocial intervention studies, \$3,125,155 but we will assess outcomes at 3-month intervals based on this rationale: baseline (enrollment), to generate consistent profiles of all enrollees at a consistent point in time and prior to implementation of the new intervention; at 3-months, very early effects, at 6-months, short-term effects; and at 12-months, the longer-term effects of ViCCY vs. HI. These 3-month intervals also will allow us to compare our results with others. Ye chose a 12-

month follow-up interval for the cost-effectiveness analysis to allow for a full year of event accrual. We will pull resource use data from the electronic medical record (EMR) in 30 day increments and validated these data during routine follow-up calls with caregivers. We expect the proposed study to require 5 years for completion.

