A series of sessions is provided with the goal of achieving a lasting effect.  In preliminary studies, we found a direct relationship between the number of sessions provided and the effect obtained,  with 10 sessions of health coaching typically being a sufficient dose.  Because maintaining contact is important to the success of stress reduction interventions,  the assigned RN will check in with caregivers between intervention sessions. We will offer booster sessions to any caregiver in the ViCCY arm who wishes to receive additional support during the 6-month intervention interval.  We will track the number of sessions and test for differential effectiveness based on the dose received. If a brief check-in call becomes an intervention session, it will be tracked for use in analysis. We will mail monthly newsletters to maximize retention (see Recruitment and Retention Plan). Because we found that early and intense contact with the coach builds the relationship, engages the participant in the treatment program,  and maximizes outcomes,  we will front-load the intervention sessions (**Figure 3**). Consistency is important for trust building, behavioral change, and growth,  so one RN health coach will be assigned to work with each caregiver for the full 6-month period. Intervention content is carefully standardized, guided by a manual with session agendas and checklist of specific content to be covered in each call, but also tailored to allow the coach to focus on caregiver needs, addressing unique and varying individual characteristics, preferences, and goals. 

Table 3. Intervention Content Derived from the Transactional Model of Stress and Coping						
Theoretical Dimension	Intervention Actions by the RN Health Coach					
Caregiving demand	Assess caregiving demand (e.g., patient behaviors, communicating with providers, feeling isolated). 12,18,194 Provide "mutual education" and cross-learning—caregivers educate the RN about the nature of their problems and the RN educates the caregiver about the purpose of health coaching and how self-care can help the caregiver.					
Primary appraisal (significance of the stressor)	Assess beliefs about HF and personal goals to determine how caregiving demand impacts caregiving burden and personal goals.					

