To assess changes in each of the primary and secondary outcomes over time, separate mixed effects regression models will be generated with SAS Proc Mixed. 265 We are not powered for secondary outcomes (e.g., stress, coping, health status), but we will examine effect sizes and confidence intervals (CIs) to determine if lack of power is driving nonsignificant results. Mixed models can account for correlation between repeated measures and handle non-excessive MAR or MCAR data better than traditional models and allow for use of time-independent and time-dependent covariates. Both random slopes and random intercepts will be modeled to represent deviations from the average, or fixed-effect, slope over time and intercept, respectively. REML will be used for parameter estimation and the most appropriate covariance structure will be examined. Scores will be analyzed as repeated observations, with mean-centered baseline outcome scores serving as a covariate. Other predictor variables will include group, assessment time, and the interaction of group time (primary effect of interest). Baseline measures and group will be analyzed as time-independent covariates. The evaluation of differences in outcome profiles over time according to group will rely on the group x time interaction terms, while differences by the balancing variables will rely on the mixed-effects modeling of higher order interaction terms. 267-270 Statistical significance for individual intervention contrasts will be evaluated for each outcome, applying the Benjamini & Hochberg method to control for the type I error rate at 5%. The Akaike information criterion (AIC) will be used to evaluate overall model fit and to select the best-fitting longitudinal change pattern. We expect the groups to be balanced on baseline characteristics due to randomization; however, imbalances that occur by chance will be adjusted for in all analyses. Time-dependent covariates of perceived stress and potential moderating effects of natural support or an intervening hospitalization will be examined in exploratory models. Using methods described above, time-specific contrasts will be estimated to evaluate differences in outcome within groups at 9 and 12 months.

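### C.15 adjusts for the dose of intervention received without limiting this to supportive models; coaching sessions in the 6-month group contrast could erase a real effect or create a false one

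*Combined protocol and SAP*

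**What the plan says.** - **C.15, item 1** deals with differential compliance, for instance when a patient's exacerbation disrupts sessions or assessments. It ends: "We will collect data on cancelled and delayed events for later analysis and adjust for delays and the dose of intervention received in analyses". No outcome, model or tier of analysis is named.
- **Intention-to-treat.** The Specific Aims state that "we will compare the efficacy of ViCCY (HI plus coaching) to HI alone to assess intervention efficacy using intent-to-treat analysis". C.3 states that "we will assess intervention efficacy at 6 months using intention-to-treat analysis". C.14 opens by applying the principle to all analyses.
- **C.14, mixed model.** The baseline score is a covariate. Then: "Other predictor variables will include group, assessment time, and the interaction of group time (primary effect of interest". Dose is not listed.
- **C.14, exploratory terms.** "Time-dependent covariates of perceived stress and potential moderating effects of natural support or an intervening hospitalization will be examined in exploratory models". Dose is not listed here either.
- **C.6, uses of dose.** "We will track the number of sessions and test for differential effectiveness based on the dose received". Also: "If a brief check-in call becomes an intervention session, it will be tracked for use in analysis". And: "We will offer booster sessions to any caregiver in the ViCCY arm who wishes to receive additional support".
- **Planned dose.** C.8, Table 4, plans 10 sessions for every ViCCY caregiver. The Specific Aims give the control arm the same health information without coaching.
- **C.14.2** uses the number and length of contacts for costing.

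**The concern.** The number of coaching sessions is close to a relabelling of the randomised arm: zero throughout control, about 10 in ViCCY. It is also determined after randomisation, and by the plan's own account it can follow prognosis. Exacerbations can interfere with sessions, boosters go to caregivers who ask for more support, and check-in calls can turn into sessions.

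Adjusting the group comparison for such a variable changes the question. Control contributes no information on the session slope, so the slope comes from ViCCY alone. The group coefficient then compares control with a ViCCY caregiver extrapolated to zero sessions. If coaching works through sessions, which C.6 reports from earlier studies, that comparison removes the effect under test. If caregivers who are doing worse take more sessions, or fewer, it produces a difference where none exists.

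Because the wording is open, whether to adjust could be decided after the data are seen.

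**Working it through.** **Inputs from the plan (C.13).** Mean neglect scores at 0, 3 and 6 months are 3.2, 1.25, 1.1 (ViCCY) and 3.2, 3.0, 2.7 (HI). SD is 2.8, first-order autocorrelation 0.3, 100 analysable per arm, 5% level (taken as two-sided). The 6-month difference is 2.7 − 1.1 = 1.6.

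**Inputs assumed, because the documents give none.** ViCCY sessions received: mean 8, SD 2.5, normally distributed; grid of mean 6 to 9 and SD 1.5 to 3.5. Correlation of sessions with the 6-month score: 0.1 or 0.2.

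**The plan's own figures.**
- Enrolment: 200/(1 − 0.20) = 250, as stated.
- Overall group effect: the SD of a three-visit mean is 2.8 × √[(3 + 2(0.3 + 0.3 + 0.09))/9] = 1.953. With difference 1.117, power is 98.1% (stated 99%).
- Time effect: 99.9% (stated 99%).
- Group by time, 2 df: 94.3% (stated 90%, from 100 simulations with Monte Carlo error of about 3 points).
- The 6-month contrast alone: SE = 2.8 × √(2/100) = 0.396, power 98.1%.

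The design reproduces, and sample size is not at issue.

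**Loss of precision.** With equal arms and zero sessions in control, the squared correlation between group and sessions is mean²/(mean² + 2SD²). The variance inflation for group is therefore 1 + mean²/(2SD²).
- Mean 8, SD 2.5: 1 + 64/12.5 = 6.12, so the SE is multiplied by 2.47.
- Mean 9.5, SD 1: 1 + 90.25/2 = 46.1.
- Exactly 10 sessions for everyone: the group effect cannot be estimated. The problem worsens as delivery approaches the plan.

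**Real effect of 1.6, 6-month ANCOVA on baseline.**
- Without sessions: SE about 0.395, power 98%.
- Benefit proportional to sessions: the slope is −1.6/8 = −0.2 per session, so the group coefficient is −1.6 − (−0.2 × 8) = 0. Simulated rejection is about 5%.
- Benefit not proportional to sessions: the estimate stays at −1.6, but SE = 0.395 × 2.47 = 0.976 and 1.6/0.976 = 1.64. Power is 37% by formula and about 36% by simulation.
- Grid corners for this second case: mean 9, SD 1.5 gives inflation 1 + 81/4.5 = 19 and power about 15%. Mean 6, SD 3.5 gives 1 + 36/24.5 = 2.47 and power about 72%.

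**No true effect, sessions correlated r with the 6-month score.** The slope within ViCCY is r × 2.8/SD, so the group coefficient shifts by r × 2.8 × mean/SD in absolute value.

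| | r = 0.1 | r = 0.2 |
|---|---|---|
| Shift, mean 8, SD 2.5 | 0.9 | 1.8 |
| Shift over the grid | 0.5 to 1.7 | 1.0 to 3.4 |
| Significant, mean 8, SD 2.5 | about 15% | about 44% |
| Significant over the grid | about 12 to 17% | about 32 to 49% |

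Simulation runs differ from these by a point or so. The shift is toward false benefit if caregivers who are doing worse take more sessions, and toward false harm if they take fewer. Without sessions in the model the rate is about 5%.

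**Repeated measures.** A simplified version of the C.14 model was also run: 3- and 6-month scores only, baseline as covariate, generalised least squares with unstructured covariance, without the random slopes and intercepts that C.14 specifies. Its 6-month contrast falls from 98% to 5% (proportional) or 50% (not). Null rejections are 10% and 28% at r = 0.1 and 0.2. The group-by-time estimate (about 0.14, SE 0.47) is identical with and without total sessions, because a covariate that is constant over visits cancels from the change between visits.

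**The case against.** The strongest reply is that C.14 governs the analysis, applies intention-to-treat throughout and lists the predictors without dose. C.6 gives dose its own test. On this reading the C.15 clause, which sits in a list of challenges, merely points to that test. The term that C.14 calls its primary effect, group by time, is untouched by total sessions. The session distribution and the correlations are assumed.

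Much of this stands. The benign reading is plausible, the group-by-time point is correct, and the figures illustrate a mechanism. A reader might infer that the sponsor has committed to putting dose in the primary model, or that the false-positive rates forecast this trial. The documents support neither: C.14 omits dose, and no session data are given.

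The reply does not secure the benign reading. Intention-to-treat fixes who is analysed and in which arm, not which covariates are barred. The C.14 list is not closed, since chance baseline imbalances are to be added in all analyses. Its exploratory-only terms leave dose out. Neither C.6 nor C.14.2 is said to be the only use of dose. The multicollinearity check in C.14 comes after database lock and prescribes no response. C.3 also assesses efficacy by the 6-month contrast, which is where the exposure lies.

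Dose might be taken to include website or book use, tracked in both arms under C.5. C.6 and C.8 favour coaching sessions, and website or book use is also measured after randomisation.

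**Conclusion.** The point holds as an unresolved conflict: C.15 gives an unconditional instruction that, if followed in the 6-month group contrast, contradicts the intention-to-treat commitment and can reverse the conclusion in either direction. It should be fixed, although C.14 as it stands does not enter dose.

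The direction of the problem follows from the design: no coaching in control, and sessions set after randomisation. Its size depends on the assumed session distribution and on how sessions relate to outcome. If sessions neither carry the effect nor follow prognosis, there is no bias, only a large loss of precision. The group-by-time term is not at risk from a total-session main effect.

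The assessment window is a separate matter. Calls may move by up to two weeks in both arms, so using actual assessment time is legitimate.

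**What to change.** - State in C.14 and C.15 that coaching-session dose, and delays or cancellations of coaching sessions, do not enter the primary or secondary intention-to-treat efficacy models. They are used only in the dose analysis of C.6, labelled supportive.
- Add that costing under C.14.2 is unaffected and that actual assessment timing may still be used.
- C.15, item 2, allows adjustment for natural support if needed, while C.14 examines it in exploratory models. State that natural support measured after randomisation stays there.

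The cost is two or three sentences. Sample size is unchanged and no new data are needed.

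Separately, and not part of the dose problem, the randomisation strata in C.4.d (caregiver sex and relationship to patient) could be named as main-effect covariates beside the baseline score. This is optional and costs two or three degrees of freedom. If the strata explain 5% or 10% of outcome variance (assumed), omitting them makes a nominal 5% test run at about 4.4% or 3.9%, which is mildly conservative.

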- **C.9. Caregiver Characteristics and Outcomes.** *On enrollment*, the RA will collect self-report data from caregivers using encrypted laptop computers. Data will be entered directly into the REDCap database as collected, with data entry screens designed to incorporate range checks and concurrent checks to minimize errors. Caregiver burden will be measured using the Dutch Objective Burden Inventory (alpha coefficient 0.81-0.84, construct validity), which measures the full range of activities required to care for HF patients (demand) as well as the burden associated with these demands. Quality of the relationship with the patient; social determinants of health; and demographic, caregiving, and clinical characteristics will be gathered from caregivers at enrollment only. *At 3, 6, 9 and 12-months* post randomization we will telephone caregivers and collect self-report data on self-care, stress, coping, and health status (**Table 5**). At 12 months we will measure QALYs. These data will be obtained by interview and entered directly into REDCap using encrypted laptop computers. Self-report instruments with demonstrated cultural-sensitivity and prior validity testing in caregiving samples were chosen, and measures are as brief as possible to minimize burden.
- **C.10. HF Patient Characteristics**. With patient consent, HF patient demographic and clinical characteristics will be abstracted from the medical record at enrollment. Duration of HF will be measured in months. All comorbid conditions will be noted and classified using the Charlson Index.  Physician ratings of New York Heart Association functional class as noted in the EMR at enrollment will be used to describe HF patients. The SF-6D will be administered to HF patients at baseline and 12 months to obtain QALYs. 

Table 5. Caregiver Outcome	e Varial	oles and Measurement			
Definition and Measure	Items	Item responses	Reliability	Validity	Comments
Self-care (behaviors undertaken to maintain health). Health Self-Care Neglect (HSCN) scale  and the short Health-promoting lifestyle profile (HPLP) II. 	10 30	HSCN dichotomous. HPLP 4-point Likert scale; higher score = more healthy behavior.	0.76 0.90	Content Criterion	The HSCN has not been widely tested so we augment this measure with the widely-used Health-promoting lifestyle profile II. To minimize burden, we will use the short form.

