Work performance [lost productivity due to time away from work (absenteeism) and reduced efficiency at work (presenteeism). 242 7-day work performance questionnaire. 243	13	Interview format. Varied (10-pt scale and dichotomous [yes/no] and number hours spent performing paid and unpaid work	0.73	Predictive Concurrent Construct	Caregivers will be interviewed at baseline, 3-, 6-, 9-, and 12-months to assess lost productivity.

**C.11. Health care utilization outcomes: Caregivers and patients.** Health care utilization of both caregivers and consenting HF patients will be obtained from the EMR for 12 months before and 12 months after randomization using a process of active surveillance **(Table 6)**. The Penn Data Store will monitor inpatient and outpatient activity and generate automated reports for tracking of mortality. As EMR data may be incomplete if a person is hospitalized outside the Penn health system, caregivers will be asked about their health care use when they are telephoned at 3, 6, 9, and 12 months. If the patient in their care has provided consent, we will also ask the caregiver about HF patient hospitalizations outside the Penn health system. We will ask about all major categories of use including provider visits, hospitalizations, emergency department (ED) visits,

diagnostic and therapeutic procedures, ambulance services, and home care services received. RAs blinded to study group will perform these assessments.

Table 6. Cos	Table 6. Cost Effectiveness Data to be Collected on Caregivers and HF Patients						
Variable	Definition and Comment	Measures					
QALYs	QALYs are derived from the SF-36 because the SF-6D based on the SF-36 is more discriminative than that derived from the SF-12. 	SF-36					
Hospital readmission rates	Risk-standardized all-cause readmission rates (RSRR) endorsed by the National Quality Forum  as a measure of hospital performance and aligns with published standards for statistical models used for calculation and public reporting of health outcomes and efficiency measures. 	EMR					
Days in the hospital	Captures the natural history of the multimorbid HF patient experience.  Used to describe the burden of disease from the individual and healthcare system perspectives  and in previous trials.  Maximal exposure of 365 days.	EMR					

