**C.14.2.** Aim 2: To estimate the cost and cost-effectiveness of ViCCY over 12 months. We hypothesize that caregivers randomized to ViCCY vs. HI only will have **H2a**: Higher QALYs measured with the SF-6D derived from the SF-36; and **H2b**: Lower health care resource use. The primary outcomes of this analysis include the difference in costs (intervention cost minus cost offsets), the difference in QALYs measured with the SF-6D, and the incremental cost effectiveness ratio (the difference in costs divided by the difference in QALYs). Costs will include both the costs of intervention implementation (number and length of intervention contacts, RN time to assess need for and delivery of the intervention, technology expenses, supervision time, and initial training). Cost offsets include the costs of health care (detailed below) and the difference in workplace productivity collected for both study groups. QALYs will be used to assess effectiveness. We hypothesize that compared to HI, ViCCY will require more resources for intervention implementation, but will reduce use of other health care resources. It is unclear if the changes in health care resource use or labor productivity will fully offset the intervention implementation costs (leading to a finding of dominance: lower cost and greater effect) or if net costs will be positive (leading to a finding of cost-effectiveness). We will follow a micro-costing approach in which all clinically relevant resources used in the study groups will be tracked and converted to costs using appropriate price weights.

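### Caregivers are dropped when the patient dies, which creates avoidable and probably informative missing data, mainly in the interview-based Aim 2 outcomes

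*Combined protocol and SAP*

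**What the plan says.** C.15, item 4, anticipates patient deaths, noting that "half of all HF patients die within 5 years", and sets the rule: "Should this occur, the caregiver will be dropped from the study". It does not say whether this ends coaching, telephone interviews, EMR surveillance or inclusion in the analysis.

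Other sections assume follow-up of every randomised caregiver and make no exception for patient death:

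- C.3: "we will assess intervention efficacy at 6 months using intention-to-treat analysis". C.14 extends intent-to-treat to all analyses.
- C.11: utilisation "will be obtained from the EMR for 12 months before and 12 months after randomization". For care outside Penn, "caregivers will be asked about their health care use when they are telephoned at 3, 6, 9, and 12 months".
- C.9: "At 12 months we will measure QALYs", from the SF-36, which is collected by telephone interview.
- Table 5: "Caregivers will be interviewed at baseline, 3-, 6-, 9-, and 12-months to assess lost productivity". C.14.2 carries this into costs: "Cost offsets include the costs of health care (detailed below) and the difference in workplace productivity collected for both study groups".
- The Retention section aims to keep participants for 12 months.

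C.14 plans covariate adjustment and shared-parameter or pattern-mixture models for informative dropout, but does not name patient death. C.13 allows 20% attrition without saying whether that includes patient deaths.

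For H3c, C.14.3 starts survival time at caregiver enrolment and groups patients by categorised caregiver outcome. It gives no visit at which improvement is scored and no rule for patients who die before it.

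**The concern.** Patient death is not loss of the randomised unit. The bereaved caregiver can still be telephoned, and the Protection Against Risk text already allows abbreviated data collection for fatigued or stressed participants.

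The consequence depends on what dropped means. If only follow-up ends, data from before the death stay in the mixed model and intent-to-treat is weakened by missing data. If the caregiver is removed from analysis, intent-to-treat is broken. Even on the milder reading, baseline is a covariate rather than an outcome in the C.14 model, so a caregiver whose patient dies before the 3-month call contributes no outcome.

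The missingness is probably informative, because bereavement plausibly changes stress, self-care, health status and work. The trial's own H3c links caregiver self-care to patient mortality, so dropping could depend on outcome. If no bereaved caregiver is followed, no model can learn post-bereavement values from the data; it can only assume them. Aim 2 would then describe 12-month QALYs, productivity and self-reported use without the period after a death, and those data cannot be collected later.

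For H3c, a patient must survive to the scoring visit for a caregiver under this rule to be scored at all. The result then turns on how unscored caregivers are coded.

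**Working it through.** **The plan's own figures.** 200 evaluable / (1 - 0.20) = 250 enrolled, as C.13 states. With C.13's means, SD 2.8 and autocorrelation 0.3, at 100 per arm and two-sided 5% (sidedness assumed), power is 98.0% for group (stated 99%), 99.9% for time (99%) and 94.2% for group by time on 2 df (90%). A baseline-to-6-month contrast gives 84.6%. The last two bracket the stated 90%, which comes from 100 iterations (Monte Carlo SE about 3 points). The sample-size claim is not in dispute.

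**Expected losses.** The only mortality input is C.15's 50% at 5 years. Assuming constant hazard, h = ln 2 / 5 per year and the loss by time t is 1 - exp(-ht). Ranges use 5% to 25% annual mortality.

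| Month | Proportion | Of 250 | Range |
|---|---|---|---|
| 3 | 3.4% | 8.5 | 3.2 to 17.3 |
| 6 | 6.7% | 16.7 | 6.3 to 33.5 |
| 9 | 9.9% | 24.7 | |
| 12 | 12.9% | 32.4 | 12.5 to 62.5 |

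- Calls lost: 8.5 + 16.7 + 24.7 + 32.4 = about 82 of 1,000 (32 to 162). After 20% other attrition, 82.3 x 0.8 = about 66 (25 to 129).
- No follow-up score at all: about 9 caregivers (3 to 17). The other 24 or so of the 32 keep at least one SF-36 from before the death.
- Follow-up time after the death: 1 - (1 - exp(-h))/h = 6.6% (2.5% to 13.1%).
- 12-month interviews, if deaths are additional to and independent of the 20%: 250 x 0.8 x 0.871 = 174 (150 to 190) instead of 200. If the 20% already includes deaths, the total is unchanged and deaths make up about 13 of the 20 points.

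**Aim 1 illustration.** Assume no coaching effect in the bereaved and equal deaths by arm. The 6-month difference is 2.7 - 1.1 = 1.6, so the shift is 0.067 x 1.6 = 0.107 points, and 0.107 / 2.8 = 0.04 SD (0.01 to 0.08). Two-sample t-test power is 98.0% at 100 per arm and 97.2% at 93 per arm.

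**Aim 2 illustration.** Each 0.05 of unseen between-arm utility difference shifts the QALY difference by 0.0662 x 0.05 = 0.003 (0.001 to 0.007). The 0.05 is an assumption; the documents give no figure.

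**H3c.** Log-rank rejection was simulated with 40 dyads, no true association and 8,000 replicates, for 30/50/70% of caregivers improving:

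| Handling of unscored caregivers | 6-month status | 12-month status |
|---|---|---|
| Counted as not improved | 2.6/16.6/41.1% | 6.1/58.1/94.5% |
| Excluded | 3.5/2.0/3.6% | no deaths left to test |

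If all caregivers are scored, rejection is 4.1/4.5/4.6%. At 50% improving, the not-improved coding gives 3.5% to 32.3% (6-month status) and 10.2% to 93.8% (12-month status) across the mortality range. About 40 x 0.129 = 5.2 deaths are expected, so power at a hazard ratio of 0.5 is about 12%.

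**The case against.** The strongest reply is that the word only needs defining. Nothing says that collected data are discarded, and C.14's commitment to intent-to-treat makes exclusion from analysis the less natural reading. The trial concerns people currently giving care, eligibility requires it, and sparing bereaved people further interviews is defensible. Table 4 and the Human Subjects text track dropout and its reasons, and C.14 plans pattern-mixture models with sensitivity analyses. The illustrated biases are small, and the utility difference behind the Aim 2 figure is assumed.

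Much of this stands as a limit on size. A while-caregiving target could be coherent, but no section states one. Tracking reasons and modelling dropout are useful, yet they cannot supply values the rule stops collecting. The Aim 1 figure is near an upper bound, since it removes all benefit even from someone bereaved the day before the call.

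Two corrections to the arithmetic are fair. Measured from the last completed call rather than from the death, unseen interview time is 82/1,000 = 8.2%, and the Aim 2 illustration becomes 0.082 x 0.05 = 0.004. If other attrition accrues linearly, about 70 rather than 66 extra calls are needed.

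On H3c, no section proposes counting unscored caregivers as not improved, and at 30% improving even that coding inflates little. A landmark gives the same log-rank result as excluding early deaths; its merit is that it is stated in advance. C.14.3 also plans GEE and frailty survival models, and Aim 3 is exploratory.

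The copy of C.14.2 reviewed breaks off mid-sentence, so some Aim 2 text may not have been visible.

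**Conclusion.** The concern holds and should be fixed. It is a problem of estimand and data completeness, not of power. About 32 of 250 caregivers (13 to 63) would leave by 12 months because of the rule, roughly half of them after the 6-month primary assessment. The effect therefore falls mainly on Aim 2, where the text reviewed gives no method for missing QALYs or productivity. EMR use may survive the rule, depending on what dropped stops. The likely effect on Aim 1 is small.

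These numbers rest on a constant hazard derived from the 5-year figure; mortality in a specialist clinic sample could differ, hence the range. That the missingness is informative is a reasoned inference, not something the documents demonstrate.

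H3c is a secondary point. Its false-positive rate is inflated only if unscored caregivers are coded as not improved. Excluding them avoids inflation but loses the deaths before the scoring visit. If bereaved caregivers were followed and scored there would be no immortal time, but bereavement itself could change self-care, so a rule would still be needed.

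**What to change.** Replace the sentence in C.15 with wording such as:

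> If the patient dies, data collection continues for willing caregivers (remaining 3-monthly calls, and EMR to 12 months). All randomised caregivers stay in the intent-to-treat analyses. Bereavement and its date are recorded as an intercurrent event, and a sensitivity analysis excludes post-bereavement data.

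The weaker alternative is to state a while-caregiving target, define dropped, and reconcile it with C.11, C.14 and the Retention section. Either way, name patient death in the C.14 missing-data text and say in C.13 whether the 20% includes it. The protocol should also say whether coaching continues after the death; that is for the investigators, and no position is taken here.

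For H3c, name the visit that defines improvement and the handling of earlier deaths. Use either a 3- or 6-month landmark with survival starting there, or caregiver self-care measured before the death as a time-dependent covariate, as C.14.3 already plans for patient QALYs.

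The cost is wording plus up to about 82 calls already in the schedule (about 66 to 70 after other attrition). Some bereaved caregivers will decline, and the calls need sensitivity. A landmark loses about 1 (3 months) or 3 (6 months) of 40 dyads and leaves about 4 or 2.5 deaths, so H3c power at a hazard ratio of 0.5 falls to about 10% or 8%.
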